11.1 Primary Endpoint

The primary endpoint for efficacy in Phase 2 will be PFS. For Phase 2, PFS is defined as time from randomization to either first disease progression (by RECIST 1.1) or death from any cause. For Phase 1, PFS is defined from the date of consent to either first disease progression by RECIST 1.1 or death from any cause.

For the purpose of analysis for patients who are alive at the time of analysis and have not had disease progression, the following rules will apply:

- (1) The patient will be censored on the date of the last tumor assessment documenting absence of progressive disease
- (2) If the patient was given antitumor treatment other than study drug treatment, the patient will be censored as of the date of the last tumor assessment prior to initiating that antitumor therapy
- (3) If the patient was removed from study for toxicity or other reason, the patient will be censored as of the date of the last tumor assessment on study.

With regard to missed tumor assessments:

- (1) In the event of one missed tumor assessment followed by a subsequent assessment of progressive disease (PD), the subsequent PD assessment qualifies as objective tumor progression.
- (2) In the event of more than one consecutive missing tumor assessment followed by a subsequent assessment of PD, the patient will be censored at the last adequate tumor assessment. If individual scans are performed on different dates, but contribute to the same overall assessment, the date of the earliest scan will be used.

The PFS distributions in the two arms will be summarized using the Kaplan-Meier method. The distributions will be compared using a stratified (by the randomization stratification factor) log-rank test at the one-sided $\alpha=0.10$ level of significance.

Additional exploratory analyses of PFS will be conducted in subgroups defined based on number of prior therapies (one, two or three), ECOG performance status, and the biomarkers TGF- β receptor III and osteopontin. The same methods are for the primary analysis (Kaplan-Meier

survival estimation, log rank tests) will be used. The effects of these covariates may also be assessed using Cox proportional hazards regression models.

The best response (CR, PR, SD or PD according to RECIST 1.1 and according to Choi criteria) for each patient with measurable disease who received at least one dose of study drug will be listed by cohort and response rate (CR or PR) between the two arms will be compared using Pearson's chi-square test or Fisher's exact test. Stable disease will be defined as lack of tumor progression lasting for 2 cycles or longer. Additional analysis will be conducted based on duration of response, defined from the time to first response (CR or PR) to disease progression and will be compared between arms using Kaplan Meier methods. Other secondary analysis would include disease stability rate (DSR) defined as the percent of subjects in ITT population with CR, PR and SD at 16 weeks, and will be compared using Pearson's chi-square test or Fisher's exact test.

The primary Phase 2 endpoint of PFS will be determined based on objective tumor assessments made by Central Radiographic Review according to RECIST version 1.1. PFS will also be determined based on investigator assessment. Treatment decisions will be made by the investigator based on application of RECIST 1.1. Supportive analyses will be performed based on investigator assessments of disease response and progression. In cases where Central Radiographic Review assessment of response conflict with investigator assessment the data will be censored as it related to the endpoint.

The clinical response of the study treatment will be assessed by a comparative evaluation of computed tomography (CT) or magnetic resonance imaging (MRI) scans prior to enrollment into the study and every 8 weeks using RECIST 1.1 (primary endpoint) or Choi criteria (secondary endpoint).

A listing will be provided for best overall response, i.e., CR, PR, SD, PD or NA (not assessable due to missing or incomplete assessments or inconsistent assessment methods) for each patient. A listing or figure will also be provided for duration of PFS and sum of the diameters for target lesions over time in patients. The listings for best overall response and PFS will compare to overall response and PFS of treatments received prior to study entry, including the most recent treatment that included a VEGF inhibitor.

12. Safety Analyses

Safety will be assessed by examining vital signs, physical exams, clinical laboratory tests, and adverse events (AEs). These analyses will be conducted on the safety population. Descriptive statistics will be provided for safety variables.

Baseline will be defined as the last available measurement prior to First Dose. Where this definition does not apply, the definition for that analysis will be specified.

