10.5. Analysis of Primary and Secondary Objectives

10.5.1. Phase 1b

For each cohort, DLTs will be summarized by category (hematologic and non-hematologic) and by MedDRA preferred term.

All AEs with an onset after initiation of treatment will be considered as treatment-emergent AEs. A preexisting condition that worsens during the treatment period will also be considered as a treatment emergent AE. All AEs will be coded by system organ class (SOC) and preferred term using NCI CTCAE (MedDRA) version 4.0.

The number and percentage of patients with the following types of treatment-emergent AEs will be summarized: common and serious AEs, AEs related to study medication, AEs resulting in study discontinuation, and clinically significant laboratory abnormalities. Non-treatment-emergent serious AEs will be described separately. Deaths will be reported with demographic information.

10.5.2. Phase 2

The primary endpoint for efficacy will be PFS, defined as time from randomization to either first disease progression (per independent radiology review of images by RECIST) or death from any cause. PFS will be censored on the day following the date of the last tumor assessment documenting absence of progressive disease for patients who do not have objective tumor progression and are still on study at the time of analysis, are given antitumor treatment other than the study treatment, are removed from study follow-up prior to documentation of objective tumor progression, died of non-cancer causes including death due to an unknown cause in the absence of documented disease progression.

The PFS distributions in the two arms will be summarized using the Kaplan-Meier method. The distributions will be compared using a stratified (by performance status) log-rank test at the one-sided $\alpha=0.10$ level of significance.

Additional exploratory analyses of PFS will be conducted in subgroups defined based on number of prior therapies (one, two or three). The same methods as for the primary analysis (Kaplan-Meier survival estimation, log rank tests) will be used. The effects of these covariates may also be assessed using Cox proportional hazards regression models.

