A hazard ratio (HR) of 0.67 is considered to be clinically relevant. Based on 1:1 randomization and the use of a one-sided log-rank test at the $\alpha=0.10$ level of significance, 115 events are required in order to have 80% power to detect a HR of 0.67. The expected PFS of patients treated with axitinib who have progressed following first line treatment with a VEGFR TKI is 4.8 months. Based on a planned accrual period of 12 months, and a minimum follow-up period of 4.3 months, approximately 150 patients will be required. Timing of the final analysis of PFS will be determined by the sponsor based on the expected total number of events that define PFS and the timing of these events, and may occur prior to the occurrence of 115 events.

5. Analysis Population

The safety population includes all patients who receive at least a portion of one dose of the study drug, TRC105 or axitinib (phase 2 portion).

The phase 2 study population for efficacy will include all randomized patients (intention to treat).

The Phase 1b study population for efficacy will include all patients who receive treatment with axitinib and TRC105.

6. General Analysis Comments

Summary statistics will include frequencies and percents of responses in each category for discrete measures; and may include means, medians, standard deviations, minimum and maximum values for continuous measures. Listings of data represented on the Case Report Form (CRF) will be provided.

SAS[®], Version 9.0 or higher or R version 2.15 or higher, will be used to perform all statistical analyses.

7. Missing Data

All data collected, including unscheduled visits, will be presented in the data listings. Summary tables will generally be limited to planned visits.

In all analyses, except for partial dates, it is expected that only observed values will be presented; no imputation of missing data will be conducted. Partial dates will be imputed according to the following table. CRFs that are not listed below are not expected to contain partial dates. CRF versions may change. Only if a change impacts the imputation of a partial date will the SAP be amended.

Planned Imputation Methods for Partial Dates

CRF	Field	Planned Imputation Method	
		Month and Year Given	Year Given
Adverse Events	Date of Onset	First of Month	Jan 01 of Year
	Date of Resolution	Last day of Month	Dec 31 of Year
Concomitant Medications	Start Date	First of Month	Jan 01 of Year
	Stop Date	Last day of Month	Dec 31 of Year

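### SAP 11.1 applies the other-therapy censoring rule only to patients who are alive and progression-free at the analysis, so censoring depends on the later outcome and can bias the primary PFS test

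*SAP*

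**What the plan says.** SAP 11.1 defines phase 2 PFS as "time from randomization to either first disease progression (by RECIST 1.1) or death from any cause". It makes no exception for events after other therapy. Three numbered censoring rules follow, under a lead-in that restricts them: "for patients who are alive at the time of analysis and have not had disease progression, the following rules will apply". The second reads "If the patient was given antitumor treatment other than study drug treatment, the patient will be censored", and the date is back-dated: "censored as of the date of the last tumor assessment prior to initiating that antitumor therapy".

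Two further SAP rules stand outside that lead-in and do reach patients with progression. One concerns missed scans: "In the event of more than one consecutive missing tumor assessment followed by a subsequent assessment of PD, the patient will be censored". The other concerns disagreement between readers: "In cases where Central Radiographic Review assessment of response conflict with investigator assessment the data will be censored".

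Protocol 10.5.2 differs. Its list of patients to be censored includes those who "are given antitumor treatment other than the study treatment, are removed from study follow-up prior to documentation of objective tumor progression", and this is not tied to being alive and progression-free at the analysis. SAP section 15 says that the plan follows the protocol version it names, and it lists no departure on this point.

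**The concern.** Take two patients who both start another therapy without documented progression. One progresses at a scan soon afterwards and is an event on that date. The other has no event by the cut-off and is cut back to the last scan before the therapy. Follow-up after the therapy therefore enters the risk set only when it ends in an event. Kaplan-Meier and the log-rank test need censoring at a given time to depend only on what has happened up to then. This rule breaks that, even if patients start other therapy entirely at random.

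The arm with more other therapy loses event-free follow-up but keeps its events, so its hazard is overstated. More use on control flatters TRC105, and more use on TRC105 hides a benefit. The trial is open-label, investigators treat on their own reading while the primary endpoint uses retrospective central review, and a need for other anticancer therapy ends study treatment. Patients can therefore start other therapy before centrally confirmed progression.

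The SAP also lets the sponsor set the final analysis date, possibly before 115 events. Under the literal rule the same patient can be censored early at one cut-off and be an event at a later one.

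**Working it through.** **Plan's own figure.** The inputs, from SAP 4.2, are HR 0.67, 80% power, 1:1 allocation and a "one-sided log-rank test at the $\alpha=0.10$ level of significance".
- Schoenfeld: 4 × (1.2816 + 0.8416)² / (ln 0.67)² = 4 × 4.508 / 0.1604 ≈ 112.4, so 113 events.
- Freedman: 4.508 × (1.67 / 0.33)² ≈ 115.4, so 116 events.

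The stated 115 is reproduced, which confirms that the test is one-sided.

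**Simulation inputs from the documents.** About 150 patients (75 per arm), control median 4.8 months, accrual 12 months, minimum follow-up 4.3 months (cut-off 12 + 4.3 = 16.3 months), scans every 56 days.

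**Assumptions, because the documents give no figures.**
- PFS is exponential and accrual is uniform.
- Progression is dated at the next scheduled scan, and 10% of PFS events are deaths.
- Other therapy starts independently of prognosis and does not change the hazard. Its rate is λp/(1 − p), so a share p start it before the underlying PFS event.
- PFS events after other therapy are recorded for all, half, a quarter or none of these patients, or only as deaths within 28 days.
- The test is an unstratified one-sided log-rank at 0.10. The HR is the one-step log-rank estimate.

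There were 10,000 runs per cell (Monte Carlo error about 0.003).

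**Results with no true difference (type I error / HR).**

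| Other therapy, control vs TRC105 | All later events recorded | Half | A quarter | Deaths within 28 days only | None | Rule 2 for every such patient |
|---|---|---|---|---|---|---|
| 20% vs 20% | 0.097 / 1.001 | 0.099 / 1.000 | 0.098 / 1.000 | 0.100 / 1.000 | 0.101 / 1.000 | 0.101 / 1.000 |
| 20% vs 10% | 0.143 / 0.951 | 0.123 / 0.971 | 0.112 / 0.983 | 0.104 / 0.994 | 0.101 / 0.996 | 0.101 / 0.996 |
| 30% vs 10% | 0.214 / 0.896 | 0.156 / 0.935 | 0.130 / 0.961 | 0.110 / 0.986 | 0.103 / 0.991 | 0.103 / 0.991 |
| 10% vs 30% | 0.038 / 1.118 | 0.060 / 1.069 | 0.074 / 1.041 | 0.088 / 1.014 | 0.092 / 1.009 | 0.092 / 1.009 |

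A separate simulation gave about 0.14 at 20% vs 10%, 0.22 to 0.23 at 30% vs 10%, and 0.03 to 0.04 at 10% vs 30%, all with full recording. Adding the missed-scan rule hardly changed these.

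**The two consistent alternatives.** Censoring every patient who starts other therapy gives the last column. Counting every event regardless of other therapy gives 0.100 / 1.003 (4,000 runs). Either choice restores the nominal level.

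**The case against.** The strongest reply is that the bias needs PFS events recorded after other therapy, and the protocol schedules little that would record them. A need for other anticancer therapy ends study treatment. Tables 9 to 11 show no scan at the 28-day follow-up visit. No survival follow-up is scheduled, and the trial ends when all patients have completed treatment. If nothing is recorded later, the literal rule is ordinary censoring. This stands as a limit on size. It does not remove the defect, because protocol 7.1.3.1 asks sites to make every effort to document progression after treatment stops. Recording is therefore possible but unquantified.

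Second, a late progression after several missed scans would be censored by the missed-scan rule. That is correct for such a patient, but progressions soon after the start of other therapy, and all recorded deaths, remain events.

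Third, no document shows that use of other therapy will differ by arm. Both arms receive axitinib, and a combination patient who cannot tolerate one drug may continue on the other. This also stands: with equal use, type I error is unaffected.

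Fourth, protocol 10.5.2 suggests that the SAP wording is loose rather than intended. That may be so, but the SAP is what gets programmed, and two programmers could reach different primary results from these texts.

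**Conclusion.** Rule 2 is wrong as written, because who is censored under it depends on what happens later, and no other SAP text corrects it. The harm is conditional on two things together: different use of other therapy by arm, and PFS events recorded afterwards.

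Under the stated assumptions, type I error runs from about 0.10 to 0.14 at 20% control vs 10% TRC105, and from about 0.10 to 0.21–0.23 at 30% vs 10%. At 10% vs 30% it falls to about 0.04 with full recording and 0.06 with half. The shares and the recording rates are assumptions.

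A reader might infer two stronger points that the documents do not support:
- That the test is biased whenever the arms differ in other therapy. It is not if no later PFS events are recorded.
- That all of the SAP's PFS censoring is confined to patients alive and progression-free. The missed-scan and reader-conflict rules are not.

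**What to change.** Take rule 2 out from under the lead-in and state it for every patient, for example: *A patient who starts non-protocol antitumor therapy before documented progression or death is censored at the last adequate tumor assessment before that therapy, whatever is recorded later.*

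Reconcile this with protocol 10.5.2, which dates censoring to the day after the last assessment, does not say that the assessment must precede the other therapy, and censors non-cancer deaths that SAP 11.1 counts as events. Record the outcome in SAP section 15.

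Add one sensitivity analysis that counts every progression and death regardless of new therapy. That alternative also holds the nominal level and could be the primary rule instead. What matters is that one rule is fixed for everyone before the analysis.

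The cost is SAP wording, one extra run and fewer primary events. At 30% vs 10% with full recording and no true difference, about 90 events are counted instead of 107. At a true HR of 0.67 the same shares give about 81 events instead of 96, and power of about 0.69 instead of 0.74 (4,000 runs, 16.3-month cut-off). Censoring deaths after missed scans is optional. This fix does not need it, and it would narrow the any-cause death component of the endpoint.

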10.2.1. Sample Size Justification

The study population for safety will include all patients receiving at least a portion of one dose of TRC105. The study population for efficacy will include all randomized patients (intention to treat). The primary endpoint is PFS and the primary analysis will compare the TRC105 and control groups using a one-sided, stratified (by performance status) log-rank test at the $\alpha=0.10$ level of significance. The primary analyses of efficacy endpoints dependent on disease assessments (PFS, ORR and DR) will be performed in the intent-to-treat (ITT) population based on results of the central review of disease response and progression. Supportive analyses will be performed based on investigator assessments of disease response and progression. Pre-planned assessments of the primary endpoint will additionally be done based on number of prior therapies (one, two or three) and other known prognostic factors.

A hazard ratio of 0.67 is considered to be clinically relevant. Based on 1:1 randomization and the use of a one-sided log-rank test at the $\alpha=0.10$ level of significance, 115 events are required in order to have 80% power to detect a hazard ratio of 0.67. The expected PFS of patients treated with axitinib who have progressed following first line treatment with a VEGFR TKI is 4.8 months. Based on a planned accrual period of 12 months, and a minimum follow-up period of 4.3 months, approximately 150 patients will be required.

An interim analysis for futility will be conducted by the DMC when 55 events have occurred. At the interim analysis, the conditional power based on the observed hazard ratio will be estimated. If the conditional power is less than 25%, the DMC may recommend to the sponsor that the study be terminated for futility. However, this interim analysis will not consider the possibility of early termination on the basis of superior efficacy.

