The best response (CR, PR, SD or PD according to RECIST 1.1 and according to Choi criteria) for each patient with measurable disease who received at least one dose of study drug will be listed by cohort and response rate (CR or PR) between the two arms will be compared by Chi-square test or Fisher exact test. Stable disease will be defined as lack of tumor progression lasting for 2 cycles or longer. Additional analysis will be conducted based on duration of response, defined from the time to first response (CR or PR) to disease progression and will be compared between arms using Kaplan Meier methods. Other secondary analysis would include disease stability rate (DSR) defined as the percent of subjects in ITT population with CR, PR and SD at 12 weeks, and will be compared by Chi-square test or Fisher exact test.

All AEs with an onset after initiation of treatment will be considered as treatment-emergent AEs. A preexisting condition that worsens during the treatment period will also be considered as a treatment emergent AE. All AEs will be coded by system organ class (SOC) and preferred term using NCI CTCAE (MedDRA) version 4.0.

The number and percentage of patients with the following types of treatment-emergent AEs will be summarized for each study arm: common and serious AEs, AEs related to study medication, AEs resulting in study discontinuation, and clinically significant laboratory abnormalities. Laboratory data will be summarized for baseline, treatment visits and change from baseline as appropriate for each arm. Non-treatment-emergent serious AEs will be described separately. Deaths will be reported with demographic information. Comparison of categorical values will be made by Chi-square or Fisher exact test and of continuous variables will be made by Student t test.

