The study population for safety will include all patients receiving at least a portion of one dose of study drug (TRC105 or axitinib). The study population for efficacy will include all randomized patients (intention to treat). The primary endpoint is PFS and the primary analysis will compare the TRC105 and control groups using a one-sided, stratified (by the randomization stratification factor) log-rank test at the $\alpha=0.10$ level of significance. The primary analyses of efficacy endpoints dependent on disease assessments (PFS, ORR and DR) will be performed in the intent-to-treat (ITT) population based on results of the central review of disease response and progression. Supportive analyses will be performed based on investigator assessments of disease response and progression. Pre-planned assessments of the primary endpoint will additionally be done based on number of prior therapies (one, two or three) and other known prognostic factors.

An interim analysis for futility will be conducted by the DMC when 55 events have occurred. At the interim analysis, the conditional power based on the observed hazard ratio (HR) will be estimated. If the conditional power is less than 25%, the DMC may recommend to the sponsor that the study be terminated for futility. However, this interim analysis will not consider the possibility of early termination on the basis of superior efficacy.

4. Sample Size Determination

4.1. Phase 1

The number of patients to be evaluated in this study is based primarily on sound clinical considerations established in dose-finding designs in Oncologic studies. This 3+3 dose escalation trial is expected to enroll approximately 18 patients. The final sample size will depend on the number of DLTs observed at the different dose levels.

4.2. Phase 2

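### SAP 3.2 assigns response rate to the ITT population, but the sentence in SAP 11.1 that sets up the between-arm comparison names only dosed patients with measurable disease

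*SAP*

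**What the plan says.** Two sets of statements bear on the ORR population.

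- **All randomised patients.** SAP 3.2: "The primary analyses of efficacy endpoints dependent on disease assessments (PFS, ORR and DR) will be performed in the intent-to-treat (ITT) population". SAP 5: "The phase 2 study population for efficacy will include all randomized patients (intention to treat". Protocol 10.2.1 agrees: "PFS, ORR and DR) will be performed in the intent-to-treat (ITT) population based on results of the central review". The protocol synopsis and protocol 10.3 are in line with this.
- **Dosed patients with measurable disease.** SAP 11.1 says best response by RECIST 1.1 and by Choi will be listed "for each patient with measurable disease who received at least one dose of study drug". The same sentence continues that "response rate (CR or PR) between the two arms will be compared using Pearson's chi-square test or Fisher's exact test". Protocol 10.5.2 has the same construction: "for each patient with measurable disease who received at least one dose of study drug will be listed by cohort".

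Later in the same SAP 11.1 paragraph the disease stability rate is defined as the "percent of subjects in ITT population with CR, PR and SD at 16 weeks". The parallel sentence in protocol 10.5.2 also names ITT for that rate.

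On unassessed patients, SAP 11.1 provides a separate listing of best overall response with a not-assessable category. The sentence carrying the comparison mentions only CR, PR, SD and PD. SAP 7 rules out imputation for anything but partial dates. Neither document says whether a patient without an evaluable post-baseline scan is a non-responder or is left out of the rate.

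**The concern.** One endpoint has two candidate denominators, and no sentence reconciles them. The statement of principle says ITT. The operational sentence, which a programmer would follow, mentions only the restricted set.

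The two conditions in that set differ in kind. Measurable disease is a baseline entry criterion (protocol 5.1.1, item 4) and should exclude few patients. Receiving a dose happens after randomisation. Protocol 2.3.3 describes the study as open label, so the decision not to start treatment can depend on the assigned arm. Removing those patients gives up the protection of randomisation for ORR, while PFS and the disease stability rate keep it.

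The silence on unassessed patients matters even if ITT is intended. Two analysts could both follow the SAP and report different ORRs, one keeping not-assessable patients in the denominator and the other dropping them.

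**Working it through.** The plan states no sample size, power or alpha for ORR, so there is no figure to reproduce. The check has two parts.

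**1. Which denominator does the comparison sentence carry?**

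- Grammatically, the restriction belongs to the listing of best response. The comparison follows in the same sentence with no population of its own.
- The next population named in the paragraph is ITT, and it is attached only to the disease stability rate. The authors wrote ITT where they wanted it there and did not write it for response rate.
- The planned phase 2 outputs include a listing (16.2.3) of patients left out of the efficacy analysis. Under strict ITT it should be empty. This is weak evidence, since the phase 1b list carries the same entry.
- Against this, SAP 3.2 and SAP 5 are explicit general rules that could fill the gap.

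The restricted reading is therefore natural but not forced.

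**2. How much could it matter?**

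Inputs:
- About 150 patients at 1:1 (SAP 4.2), so 150/2 = 75 per arm.
- Control responders: assumed 15, since 15/75 = 20.0% is close to the 19.4% for axitinib in protocol Table 3.
- TRC105 responders: assumed 25, so 25/75 = 33.3%.
- Undosed patients, *k*: not given in the documents. Range taken as 0 to 10 of 75, first in the control arm only.

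Formulas: ITT rate = responders/75; dosed-only rate = responders/(75 − *k*). Undosed patients are assumed to have no response. P-values are two-sided Pearson chi-square without continuity correction.

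| Undosed controls | Control ORR | TRC105 ORR | Difference (points) | p |
|---|---|---|---|---|
| 0 (same as ITT) | 15/75 = 20.0% | 33.3% | 13.3 | 0.065 |
| 2 | 15/73 = 20.5% | 33.3% | 12.8 | 0.080 |
| 4 | 15/71 = 21.1% | 33.3% | 12.2 | 0.098 |
| 6 | 15/69 = 21.7% | 33.3% | 11.6 | 0.121 |
| 8 | 15/67 = 22.4% | 33.3% | 10.9 | 0.148 |
| 10 | 15/65 = 23.1% | 33.3% | 10.3 | 0.180 |

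Each undosed patient adds about 0.3 points to that arm's rate: (23.1 − 20.0)/10 = 0.31.

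Reversing the losses reverses the direction. With 4 undosed patients in the TRC105 arm only, its rate is 25/71 = 35.2% and the difference is 35.2 − 20.0 = 15.2 points. With 10 it is 25/65 = 38.5% and the difference is 18.5 points.

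**The case against.** The best defence is that there is no conflict: the restriction governs a listing, the comparison names no population, and SAP 3.2 and SAP 5 supply ITT by name. On that reading the plan already lists best response in treated patients and compares ORR in everyone randomised. The reading is available, so a reader who infers that SAP 11.1 definitely drops untreated patients goes further than the text allows. It is not the evident reading, though, because ITT is written out for the disease stability rate in the same paragraph. It also leaves the handling of unassessed patients unstated.

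A reader might also infer that central review could remove patients it judges to have no measurable disease, and so widen the gap between denominators. The documents do not support this. Measurable disease is an entry criterion, protocol 7.1.1 has the investigator categorise lesions at screening, and neither document lets the central reader redefine the ORR denominator.

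Nor can the wording be read as favouring TRC105. If open-label disappointment makes control patients leave before dosing, a dosed-only denominator raises the control rate and works against TRC105.

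Finally, the stakes are limited. ORR is a secondary objective, framed as estimation with no alpha or power, and the primary PFS analysis is assigned to ITT. This stands, and it lowers the severity.

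**Conclusion.** The point holds as an unresolved inconsistency. Both documents assign ORR to ITT, yet the sentence specifying the comparison carries only a dosed-and-measurable restriction. Only the dosing condition is post-randomisation. The missing non-responder rule is a second gap that remains on either reading.

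The likely size is small: about 0.3 points of ORR per undosed patient in an arm of 75 at a 20% rate, and zero if everyone is dosed. Over the assumed range of 0 to 10 undosed controls, control ORR moves from 20.0% to 23.1%. The p-values illustrate sensitivity only, since they rest on the assumed 15 and 25 responders and on all losses falling in one arm. The direction depends on which arm loses patients, so the denominator should be fixed before the data are seen. Severity is low to moderate, with moderate confidence because an ITT reading of the comparison is possible.

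**What to change.** In SAP 11.1 and protocol 10.5.2, split the sentence in two.

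- **Comparison:** state that ORR by RECIST 1.1 and by Choi is compared between arms in all randomised patients, with those never dosed, without a post-baseline scan, or not evaluable counted as non-responders.
- **Listing or sensitivity analysis:** keep the dosed and measurable-disease set here, labelled as supportive. Say that a dose of either drug satisfies the condition: SAP 5 counts TRC105 or axitinib as study drug, while SAP 12.2 names axitinib separately from it.

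The cost is wording only, with no new data or extra patients. The reported ORR will be slightly lower than in a dosed-only set, for example 20.0% rather than 21.1% in the four-undosed illustration.
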